The sodium-glucose cotransporter-2 (SGLT2) is selectively expressed in the human kidney, where it executes reabsorption of filtered glucose with a high capacity. As a therapeutic target, SGLT2 has been successfully engaged by orally active, selective agents. SGLT2 inhibition (SGLT2i) has a range of known physiological effects: Glycosuria, natriuresis, plasma volume reduction, blood pressure reduction, increased lipid oxidation and ketogenesis (2). However, only few studies have described renal physiologic effects of SGLT2 inhibition in humans, where it has been observed that hyperfiltration and renal plasma flow is reduced during clamped euglycemia in type 1 diabetes (3).

SGLT2i have been observed to reduce cardiovascular mortality and to be associated with slower progression of diabetic kidney disease in the EMPA-REG-trial (4, 5); to reduce risk of cardiovascular events and kidney failure in the CREDENCE-trial (6); to slow progression of albuminuria in the CANVAS-trial (7); and to reduce the risk of renal events in the DECLARE-trial (8). The SGLT2 inhibitor dapagliflozin, used in the DECLARE study, reach peak plasma concentration after two hours and based on glucose excretion, the renal effects seem to be present after a few hours. The half-life is approximately 17 hours (9). The exact mechanisms of the beneficial effects of SGLT2 inhibition in diabetes is still unknown, but several hypotheses have been suggested. Hypoxia might play an important role.

Renal hypoxia

The kidneys have a high oxygen consumption, needed for reabsorption of filtered solutes, mainly sodium. While the renal cortex has a high perfusion, the renal medulla has a low

perfusion and at the same time a high oxygen demand needed for sodium reabsorption in the ascending loop of Henle, making it more prone to hypoxia. The presence of hypoxia has been demonstrated in diabetic kidney disease compared to age-matched healthy controls (10). At the same time, there is strong evidence of tissue hypoxia playing a central pathogenic role in the development of chronic diabetic kidney disease (11, 12). This is supported by a recent study showing that renal cortical hypoxia predicts decline in renal function in subjects with chronic kidney disease (13).

In diabetes, a number of factors can act together and increase the risk of renal hypoxia (14):

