We hypothesize that SGLT2 inhibition acutely reduces the kidneys demand for oxygen by reducing renal metabolism due to blocked sodium-glucose transportation, and hyperfiltration. We hypothesize that the following changes can be demonstrated after institution of SGLT2 inhibition:

- 1) Lowering of renal artery flow (PC-MRI)
- 2) Lowering of renal cortical perfusion and the ratio of cortical/medullary perfusion (ASL-MRI)
- 3) Better medullary oxygenation: Lowering of the renal medulla T_2^* (BOLD-MRI)
- 4) Decrease of renal oxygen consumption (Q-flow combined with measurement of BOLD in renal artery and vein)

We further hypothesize that autonomic function will improve, and that peripheral blood oxygenation and mitochondrial function will both increase after institution of SGLT2 inhibition.

Study population

Fifteen healthy controls recruited through an advertisement in the local newspapers and 15 persons with type 1 diabetes recruited from Steno Diabetes Center Copenhagen according to the study in-and exclusion criteria.

Inclusion criteria healthy controls:

- Written informed consent must be provided before participation
- Male or female patients > 18 years of age
- Capable of lying in a MR-scanner for two hours

Inclusion criteria persons with type 1 diabetes:

- Written informed consent must be provided before participation
- Male or female patients >18 years of age with a diagnosis of type 1 diabetes (WHO criteria)
- Urinary albumin creatinine ratio (UACR) ≥ 30 mg/g in 2 out of 3 consecutive samples (albuminuria) prior to randomization assessed from electronic laboratory database.
- Capable of lying in a MR-scanner for two hours

Exclusion criteria for all:

- Non-diabetic kidney disease as indicated by medical history and/or laboratory findings
- Renal failure (eGFR<15 ml/min/1.73m²), dialysis or kidney transplantation
- Treatment with beta-blocking medication
- Uncontrolled arrhythmia, 2. or 3. degree AV-block or sick sinus syndrome - assessed from a standard 12-lead electrocardiogram
- Pregnancy or breastfeeding (urine HCG is performed on all fertile women)
- Systolic blood pressure < 90 or > 200 mmHg
- Patients who, in the judgement of the investigator, is incapable of participating
- Exclusion criteria for MRI
 - Claustrophobia
 - Known heart disease

- Known lung disease
- Have had surgery the past six weeks
- Have foreign bodies of metal in the body (e.g. pacemaker, metal plates, metal screws)

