Information about civil registration number, phone number, address, diagnosis of T1D and historic levels of urine albumin on outpatients at Steno Diabetes Center Copenhagen is provided by the treatment-responsible doctor and passed on to the study investigator. This information is used for identifying possible participants and recruitment. First contact will be a letter containing the written participant information and the brochure: "Your rights as a participant in biomedical research". In the letter, possible participants will be invited to the information meeting at Steno Diabetes Center Copenhagen. The letter contains telephone number and email for the project-responsible doctor. Non-responders will be followed up by a telephone contact approximately two weeks later. All who wish to participate in the study are invited for an information visit.

Healthy controls will be recruited by advertisement in the local newspapers. In the advertisement, there will be phone number and email of the investigators for contact.

Endpoints

Primary end-point

- Renal oxygenation (T_2^*)

Exploratory end-points

[figure not shown]
- Renal cortical and medullary perfusion
- Renal artery flow
- Renal oxygen consumption
- Peripheral capillary oxygen saturation (SpO_2)
- Arterial blood gasses
 - Arterial blood oxygen partial pressure (PaO_2)

- Arterial blood oxygen saturation (SaO₂)
- PBMC mitochondrial function
- Circulating inflammatory markers
- Baroreflex sensitivity

Study design

Randomized, double blinded, placebo-controlled, cross-over intervention study in patients with type 1 diabetes. Baseline results will be compared to healthy controls.

Figure 1

Flowchart of study design. Healthy controls (CON) will only come for baseline measurements on V1 and V2, except blood gas analysis, which will only be done in randomized patients.

Patients with type 1 diabetes (T1D) will be randomized to SGLT2i or placebo for Visits 1+2 and crossed over for Visits 3+4.

Comparative treatment regimes

Patients in the active arm will be treated with dapagliflozin 50 mg once on site for V2 and once at home on the evening before V3.

Randomization and blinding

Patients will be randomly assigned in a 1:1 ratio to one of the following groups:

- Dapagliflozin for V2 and V3 and placebo for V4 and V5
- Placebo for V2 and V3 and dapagliflozin for V4 and V5

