Mitochondrial function		x		x		x
Inflammatory markers		x		x		x
Baroreflex sensitivity		x		x		x
Kidney MRI			x		x	
Pulse oximetry			x		x	
Blood gas analysis			x		x	
Safety						
Adverse events			x	x	x	x
Study medication						
Drug accountability				x		x

Study timetable for randomized patients. SDCC = Steno Diabetes Center Copenhagen, RHG = Rigshospitalet Glostrup.

Assessment of efficacy

In order to assess the acute physiological response of inhibiting SGLT2 in the proximal tubule, kidney MRI parameters, pulse oximetry and blood gas analysis are obtained before intervention (baseline), three hours after intervention and six hours after intervention. In order to assess the subacute, systemic physiological response, PBMC mitochondrial function, inflammatory markers and baroreflex sensitivity are obtained before intervention (baseline) and 12 hours after intervention. Baseline levels will be compared to those of healthy controls.

Response to dapagliflozin in outcomes in randomized patients will be compared to response to placebo.

Assessment of safety

Definition of SAE, SAR and SUSAR

Serious Adverse Event (SAE):

A Serious Adverse event is an experience that treatment results in any of the following:

- Results in death
- Is life threatening (note: the term life-threatening refers to an event in which the patient was at risk of death at the time of the event; it does not refer to an event which hypothetically might have caused death if it was more severe)
- Requires inpatient hospitalization or results in prolongation of existing hospitalization
- Results in persistent or significant disability/incapacity
- Is a congenital anomaly/birth defect, or
- Is an important medical event that may not result in death, be life-threatening, or require hospitalisation may be considered a serious adverse event when, based upon appropriate medical judgement, they may jeopardise the patient or subject and may require medical or surgical intervention to prevent one of the outcomes listed in this definition.
- Suspicion of transmission of infectious agents must always be considered an SAE.

Serious Adverse Reaction (SAR):

A SAE for which a causal relationship to the study medication is at least possible i.e. a causal relationship is conceivable and cannot be dismissed.

Suspected Unexpected Serious Adverse Reaction (SUSAR):

A SAE which is unexpected and regarded as possibly or probably related to the study medication by the Investigator.

Reporting of SAE SAR and SUSAR

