All characteristics will be presented as means with standard deviation (SD) or if skewed distributions, as medians with interquartile range (IQR). For baseline characteristics, chi-squared test and Fischer's exact test will be used when appropriate. For testing group differences, unpaired student's t-test will be used. For testing the effect of the intervention, linear regressions analyses will be performed adjusting for baseline values of outcome variables. To fulfil the requirement of a normal distribution of the model residuals, determinants will be log-transformed where appropriate. Statistical significance is inferred as a two-tailed P-value < 0.05 . All analyses will be performed in SAS enterprise 7.1.

Data management

Source data identification and source data verification

All clinical study information in this study will be recorded, handled, and stored in a way that allows it accurate reporting, interpretation and verification.

Sponsor/investigator will provide direct access to source data/documents for study related monitoring, audit, IEC/IRB review, and regulatory inspection. Sponsor has made an agreement with the GCP-unit at the University of Copenhagen, Denmark, who will be monitoring the study in accordance with the ICH guidelines for GCP.

Subject data protection

There will be a transfer of information from the doctor responsible for the person in the clinic to the doctor responsible for the research of relevance to study participation and safety in the personal record. All information on study subjects is protected according to law on processing of personal data and the law of health. None of the study related blood samples or data will be stored or analyzed in countries outside the EU.

Data handling

Before initiating the study acceptance from the Danish Data Protection Agency will be obtained. A separate case report form (CRF) will be prepared for each study participant. All health-related matters and sensitive personal data will be handled in accordance with the Danish "act on Processing of Personal Data".

All health-related matters and sensitive personal data (CRF, blood test result etc.) will be depersonalized. All participants will be given a study number referring to their personal information, which will be stored securely and separately. Adequate blinding of all personal data during data processing and publication will be ensured.

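### The secondary baseline comparison of type 1 diabetes patients with healthy controls is an unadjusted t-test without matching, so an age or sex imbalance could be misread as a difference due to diabetes

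*Combined protocol and SAP*

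**What the plan says.** The Study design section states: "Baseline results will be compared to healthy controls". Assessment of efficacy repeats it after listing the MRI, oximetry, blood gas, mitochondrial, inflammatory and baroreflex measurements: "Baseline levels will be compared to those of healthy controls". (Blood gases are not taken in controls.)

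The two groups arrive by different routes. Under Recruitment, "Healthy controls will be recruited by advertisement in the local newspapers". Patients are outpatients of one specialist diabetes centre and must have albuminuria. The age and sex criterion for controls is "Male or female patients > 18 years of age", and the patients' criterion has the same limits. Controls are also excluded for clinically significant disease in a long list of organ systems.

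The Analysis section under Statistical considerations has two relevant sentences. The first is "For testing group differences, unpaired student's t-test will be used". The second reserves regression for the treatment effect: "For testing the effect of the intervention, linear regressions analyses will be performed adjusting for baseline values of outcome variables". The same section says that characteristics will be presented, and it names chi-squared and Fisher's exact tests for baseline characteristics. Demographic information is collected at Visit 1.

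No section provides matching, quotas, stratification or covariate adjustment for patients versus controls. Matching is mentioned once, in the Background, where an earlier study is said to have found hypoxia "demonstrated in diabetic kidney disease compared to age-matched healthy controls".

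**The concern.** Half of those enrolled (15 of 30) are controls, and the baseline comparison is the only use the plan makes of them. Nothing in the design keeps the groups alike in age or sex, and randomisation does not protect a comparison between patients and volunteers. If age or sex is related to T2*, perfusion, mitochondrial function, inflammatory markers or baroreflex sensitivity, any imbalance becomes bias in the group difference. The t-test measures that difference correctly as a difference between two samples. The risk is in reading it as something diabetes has caused.

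**Working it through.** **Inputs from the documents.** Sample size section: medullary T2* mean 23, SD 4; improvement 20%; power 80%; type 1 error 5%; 13 per group required, 15 planned. Analysis section: two-tailed test at 0.05.

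**The plan's own figure.** The difference is 0.20 × 23 = 4.6, or 4.6/4 = 1.15 SD. For an unpaired two-sided t-test with n per group, the noncentrality is 1.15 × √(n/2) on 2n − 2 degrees of freedom. Power is 76.8% at n = 12, 80.3% at n = 13 and 86.0% at n = 15. The stated 13 per group is reproduced.

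**Assumptions, because the documents give no figures.** D is the difference in mean age between the groups, in SDs of age. r is the within-group correlation of age with the outcome. The ranges are D = 0.5 to 1.0 and r = 0.3 to 0.5. There is no true disease effect.

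**False-positive rate of the planned test.** Bias in outcome SDs is r × D. In T2* units it is r × D × 4. The noncentrality is r × D × √(15/2) = r × D × 2.739, on 28 degrees of freedom.

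| r | D | Bias (SD) | Bias (T2* units) | Rejection rate |
|---|---|---|---|---|
| 0.3 | 0.5 | 0.15 | 0.6 | 6.8% |
| 0.5 | 0.5 | 0.25 | 1.0 | 10.1% |
| 0.3 | 1.0 | 0.30 | 1.2 | 12.5% |
| 0.5 | 1.0 | 0.50 | 2.0 | 26.2% |

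**The adjusted analysis.** In simulations of 15 v 15 with a linear age effect, regression on group, age and sex rejected about 5% of the time over the same range.

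**Would the baseline table give warning?** A t-test of age at 15 v 15 has noncentrality D × 2.739. Its power is 26% at D = 0.5 and 75% at D = 1.0.

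**Cost of adjusting.** Residual degrees of freedom fall from 30 − 2 = 28 to 30 − 4 = 26. An age gap also makes group and age collinear. This multiplies the variance of the group estimate by about 1 + D²/4, which is 1.25 at D = 1.0. Explaining part of the outcome offsets this by 1 − r², which is 0.91 at r = 0.3, so the net factor is about 1.25 × 0.91 = 1.14. Simulated power for a 4.6-unit difference with group, age and sex in the model is then about 77%, against 86% for the planned test without imbalance.

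**Not quantified.** No sex imbalance was modelled. The same reasoning applies, but the documents give nothing to size it.

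**The case against.** The strongest reply is about scope. The primary aim, the hypotheses and the sample size goal all concern the effect of SGLT2 inhibition in type 1 diabetes. The patient-control comparison appears in no aim or hypothesis and takes up two short sentences. That stands. A reader might infer that the primary result is confounded; it is not, because dapagliflozin and placebo are compared within the same randomised patients.

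Three other inferences also go too far.

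- *The plan attributes the difference to diabetes.* It says only that levels will be compared.
- *Demographic data are ignored.* Characteristics will be presented and tested, so a gross imbalance would be visible. The power figures show that such a test is a weak safeguard, and covariates added after seeing the table would not be prespecified.
- *The protocol commits itself to age matching.* The Background sentence describes one cited study. It is neither a design commitment nor shown to address the same question.

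It can also be said that the Analysis section does not name the groups to which the t-test applies. Patients versus controls is the natural reading, because the intervention has its own sentence and this is the only planned unpaired comparison of outcomes. If something else was meant, the comparison has no stated method, which also needs correcting.

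Finally, adjustment is not free, and the 5% error rate assumes a linear age effect and no other confounder. Both points stand.

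**Conclusion.** The gap is real and confined to a secondary, non-randomised comparison. The omission of matching and adjustment is plain from the text. The size of any harm is not, because it rests on assumed values. With an age gap of 0.5 to 1.0 SD and a correlation of 0.3 to 0.5, the false-positive rate is about 7% to 26% instead of 5%. With a smaller gap or a weaker correlation the inflation would be slight. A reader might extrapolate to error rates of 50% or more. These need a bias of about 0.75 SD, for example a 1.5 SD age gap at correlation 0.5, and nothing in the documents supports a gap that large. No sample size figure changes.

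**What to change.** In the Analysis section, add for the patient-control comparison: 'Baseline differences between patients and healthy controls will be estimated by linear regression with group, age and sex as covariates; the unadjusted difference will be shown as supportive. This comparison is exploratory.'

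Where recruitment allows, select from the responding volunteers those similar to the patients in age and sex. This matters because regression cannot recover the precision lost to an age gap, and it extrapolates if the age ranges barely overlap.

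The cost is a sentence or two of wording and two residual degrees of freedom, with no new measurements. If the groups do differ in age, the adjusted estimate will be less precise, as shown in the working. Selecting similar volunteers may slow control recruitment.

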Scanning will be performed on a 3-T Philips Achieva scanner using the scanners body transmit and a four-element SENSE cardiac receive coil. Subjects will be scanned using MRI sequences to map ASL perfusion and BOLD T_2^* in the kidneys and to measure flood flow in the renal artery. Renal oxygen consumption will be measured using Q-flow combined with measurement of BOLD in the renal artery and vein. All measurements will be performed twice.

Mitochondrial function

Mitochondrial function will be quantified by using the Seahorse 96XF Analyzer (Agilent Technologies, Santa Clara, CA, USA) that can measure oxygen consumption rate and extracellular flux in real time in a 96-well plate in intact peripheral blood monocytes (PBMCs). Extracellular flux is changes in oxygen and proton concentrations in the media surrounding the PBMCs. From this, the relative state of aerobic and glycolytic metabolism can be

determined. Thus, the Seahorse assays can quantify enzyme defects, including oxidative phosphorylation, glycolytic pathway abnormalities and fatty acid oxidation pathway abnormalities (21).

Circulating inflammatory markers

Inflammatory markers will be measured on venous blood with a validated assay including 92 inflammation-related human protein biomarkers simultaneously (Olink, Uppsala, Sweden) (22).

Baroreflex sensitivity

Baroreflex sensitivity is defined as the change in heart-rate in relation to change in blood pressure. It is considered a sensitive measurement of cardiovascular autonomic function (19). Baroreflex sensitivity will be determined from spontaneous fluctuations in the RR interval and systolic blood pressure. We will use a method earlier described in detail (23, 24).

Blood samples

From healthy controls, a total of 21 ml of blood will be taken at V1. From randomized patients, a total of 21 ml of blood will be taken at V1, 3 ml blood at V2, 11 ml blood at V3, 3 ml blood at V4 and 11 ml blood at V5. The material will only be used for analysis in the Astronaut study and will be destroyed at the end of the study.

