Clinical chemistry will include measurement of p-HbA1c, p-potassium, p-sodium, p-creatinine, p-albumin, haemoglobin, leucocytes, thrombocytes, haematocrit, p-ALT, p-INR (international normalized ratio), p-lipids (total-, HDL-, and LDL cholesterol and triglycerides). Kidney function (eGFR) will be calculated using the CKD-EPI equation from p-creatinine. Blood samples for clinical chemistry will be analysed on the day of collection and destroyed immediately after.

Peripheral blood monocytes will be purified from blood to examine mitochondrial function at Steno Diabetes Center Copenhagen on V1, V3 and V5. Samples will be analysed on the day of collection and destroyed immediately after.

A research biobank of 4 ml blood per participant will be used for analysis of inflammatory markers. A research biobank means that the samples are frozen, analysed by the end of the study (February 1st 2022) and hereafter destroyed.

Blood gas analysis include arterial blood oxygen partial pressure (PaO₂) and arterial blood oxygen saturation (SaO₂). Blood gas analysis will be performed on site at Rigshospitalet Glostrup on V2 and V4. Samples will be analysed on the day of collection and destroyed immediately after. Blood gas analysis will only be performed on randomized patients.

[figure not shown]
Biobank for unspecified future research

Study participants will be asked if they are willing to donate blood and urine to a biobank for unspecified future research. This biological material will only be used for future research after specific approval from the regional ethical committees.

Study visits

Please note that healthy controls will only participate for the information meeting, V1 and the baseline measurements of V2, except from blood gas analysis. Figure 2 shows an overview of study visits.

Figure 2

Overview of study visits. Patients with type 1 diabetes come for information visit and V1-V5.

Healthy controls come for information visit and baseline measurements of V1 and V2, except blood gas analysis.

BP = blood pressure, MRI = Magnetic resonance imaging, SGLT2i = Sodium-glucose cotransporter-2 inhibitor.

Information meeting (day 0) at Steno Diabetes Center Copenhagen

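### The stated model for the treatment effect, linear regression adjusted for baseline, does not use the cross-over pairing and leaves the handling of two post-dose times and duplicate scans open

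*Combined protocol and SAP*

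**What the plan says.** The Study design section describes a randomised, placebo-controlled "cross-over intervention study in patients with type 1 diabetes. Baseline results will be compared to healthy controls". Each patient takes dapagliflozin in one period and placebo in the other, with 1:1 allocation to the two orders.

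The measurement schedule has two forms:

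- **Kidney MRI, pulse oximetry and blood gases** (V2 and V4). Under Assessment of efficacy these "are obtained before intervention (baseline), three hours after intervention and six hours after intervention". Each period therefore has its own baseline. Of the MRI, the Methods section adds: "All measurements will be performed twice".
- **Test battery A** (mitochondrial function, inflammatory markers, baroreflex sensitivity). For the first of these, Blood samples states: "Peripheral blood monocytes will be purified from blood to examine mitochondrial function at Steno Diabetes Center Copenhagen on V1, V3 and V5". The visit timetable gives the same three visits for the other two. V1 is the only baseline.

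On the comparison itself, Assessment of efficacy says: "Response to dapagliflozin in outcomes in randomized patients will be compared to response to placebo". The Analysis section gives one sentence on the model: "For testing the effect of the intervention, linear regressions analyses will be performed adjusting for baseline values of outcome variables". The only other comparative test it names for continuous data is unpaired: "For testing group differences, unpaired student's t-test will be used". To obtain normally distributed residuals, "determinants will be log-transformed where appropriate".

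**The concern.** Two observations from the same patient are correlated. A regression that contains only treatment and baseline treats them as if they came from different people. Nothing in the plan adds a patient effect, a within-patient difference or a period term.

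The plan also does not say which T2* value is tested. Each patient yields 2 periods x 2 times x 2 measurements = 8 post-dose values. An analyst could build 30, 60 or 120 rows from 15 patients and comply with the sentence each time.

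At stake are the width of the intervals for test battery A, the true type I error of the primary MRI test, and the freedom to choose the time point or row structure after seeing the data.

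**Working it through.** **Inputs from the documents.** 15 patients; medullary T2* 23 ± 4; a 20% effect, so 0.20 x 23 = 4.6; two-sided 5%; 80% power; 13 per group (Sample size and Analysis).

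**Assumptions, because the documents give no variance components.** Orders split 8/7; patient share of total variance p from 0.3 to 0.8; scan-day share of the remainder from 0 to 0.9.

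**1. The plan's own figure.** For an unpaired comparison, n = 2(1.960 + 0.842)² x 4²/4.6² = 11.9, so 12 per group by the normal approximation. The exact t calculation gives 76.8% power at 12 and 80.3% at 13. The stated 13 is thus an unpaired calculation, and pairing is used nowhere in the statistical section. The planned number is not undermined: a paired t-test with 15 patients has 83.3% power at within-patient correlation 0 and 98.5% at 0.5.

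**2. Test battery A.** Scale the outcome variance to 1, with correlation ρ between any two visits. After adjustment for V1:

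- residual variance of a row: V = 1 − ρ²
- residual covariance between V3 and V5 of one patient: C = ρ(1 − ρ)
- variance the model reports: (2/15)V; true variance: (2/15)(V − C) = (2/15)(1 − ρ)
- reported SE / true SE = √[(1 − ρ²)/(1 − ρ)] = √(1 + ρ)

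| ρ | √(1 + ρ) | approximate type I error, 2[1 − Φ(1.96√(1 + ρ))] |
|---|---|---|
| 0.3 | 1.14 | 2.5% |
| 0.5 | 1.22 | 1.6% |
| 0.8 | 1.34 | 0.9% |

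Simulation with 15 patients (20,000 runs) gives an SE 12-33% too wide and type I error 1.2-2.8%, against 4.8-5.2% for a within-patient analysis. For an assumed effect of 0.8 SD at ρ = 0.5, power is 72% against 81%.

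**3. MRI, one post-dose value per period (30 rows).** The baseline is now specific to the period. Let r be the correlation of baseline and post-dose value on the same day, so that r = p plus the scan-day variance. Then V = 1 − r² and C = p(1 − r)².

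- p = 0.5, no scan-day variance, r = 0.5: V = 0.75, C = 0.125, SE ratio √(0.75/0.625) = 1.10.
- p = 0.5, scan-day variance 0.3, r = 0.8: V = 0.36, C = 0.02, SE ratio √(0.36/0.34) = 1.03.

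The ignored covariance is small. Simulation over 48 scenarios gives SE ratios of 0.99-1.11 and type I error of 3.0-5.4%. Power at 4.6 is about 90-100% with either analysis.

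Efficiency is a separate matter, because the slope is driven by differences between patients. Take p = 0.8 and no scan-day variance. The slope is about 0.8, whereas within a patient the baseline carries no information about the same day's post-dose value. Relative to the within-patient SE, the true SE is √(1 + 0.8²) = 1.28 for one time, and √[(0.5 + 0.64)/0.5] = 1.51 for the mean of two. The simulated range is 0.97-1.26 for one time and up to 1.5 for the mean.

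**4. MRI, rows stacked.** The +3 h and +6 h residuals of one day have covariance D = r(1 − r). With 60 rows, true variance / reported variance = 1 + (D − 2C)/V. For p = 0.5 and scan-day variance 0.3 this is 1 + (0.16 − 0.04)/0.36 = 1.33. Type I error is then about 2[1 − Φ(1.96/√1.33)] = 9.0%. Simulated ranges:

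| Rows | Type I error |
|---|---|
| 60 (times stacked) | 4.0-11.5% |
| 120 (times and duplicates stacked) | about 9-26% |
| Within-patient difference, period intercept, baseline difference | 4.2-5.8% |

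**5. Sensitivity to the variance structure.** A second simulation added patient and scan-day components after dosing that the baseline does not share. The baseline-adjusted regression on 30 rows (mean of both times) then had type I error of 0.1-3.5%. With 60 rows it was 1.2-12.3%, with 120 rows 6.6-26.5%, and for the within-patient analysis 4.4-5.4%.

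**The case against.** The strongest reply is that the plan is brief rather than wrong. One generic sentence on linear regression does not exclude a patient term or a regression on within-patient differences. Comparing response to dapagliflozin with response to placebo in the randomised patients fits a paired reading, and the unpaired t-test most naturally belongs to the comparison with healthy controls. On the simplest reading the primary test is close to nominal or conservative and well powered. Stacking has no support in the text. Test battery A is exploratory, and its error is on the conservative side.

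Much of this stands. The stacked figures show what the wording permits, not what is planned, and they should not set the weight of the point. The documents do not say why a cross-over was chosen, so no argument rests on that. It also stands that the remedy could be simpler than a mixed model.

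It does not remove the point. No section supplies the missing terms, and regression with adjustment for baseline ordinarily means a model without a patient effect. For test battery A that model gives wrong standard errors on any variance assumption with positive within-patient correlation. Even an analyst who adds the patient must still choose between +3 h, +6 h and their mean.

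**Conclusion.** The concern holds and should be fixed. As written, the model is wrong for test battery A: standard errors are 12-33% too wide for correlations of 0.3-0.8, with a matching loss of power. For the primary T2* endpoint the practical cost is small if one value per patient and period is used, apart from lost precision in some variance structures. The type I error exceeds 5% materially only if correlated rows are stacked, which the plan leaves open.

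The omission itself is certain. The sizes are not, because they depend on variance components, correlations and, for test battery A, an effect size that the documents do not give. The sample size of 15 is not called into question. The log-transformation wording is a minor slip: it names the predictors, whereas the usual remedy for a skewed outcome is to transform the outcome.

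**What to change.** Amend the Analysis section before unblinding:

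1. Average the duplicate MRI measurements to one value per session.
2. Name one primary contrast for medullary T2*, for example the treatment difference averaged over +3 h and +6 h.
3. For MRI, oximetry and blood gases, fit a cross-over mixed model. Fixed effects: treatment, period, time, treatment by time, and baseline. Random effects: patient and patient within period. Use Kenward-Roger degrees of freedom.
4. Enter the V2/V4 baseline as two terms, the patient's mean and the period's deviation from it. With one common slope the efficiency loss remains. In the worst case above (p = 0.8, no scan-day variance) the true SE was 0.62 for ordinary regression, 0.61 for a mixed model with a common slope and 0.41 with the split baseline. With the split baseline, type I error was 4.6-6.2% over nine scenarios.
5. For test battery A, compare V3 with V5 within patient, with a period term.
6. State that skewed outcomes are log-transformed.

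A simpler alternative to items 3 and 4 is to regress the within-patient difference on treatment order and the baseline difference, with an intercept for period. The cost is plan wording, a few lines of SAS and a few degrees of freedom. No extra data or visits are needed.
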